STU#:

PROTOCOL TITLE: Transcutaneous electrical nerve stimulation (TENS) for pain control during cervical dilator placement prior to dilation and evacuation: A randomized controlled trial

PRINCIPAL INVESTIGATOR:

[name], MPH
[name]
[name]
[name]
Department of OB/Gyn
[contact]

VERSION NUMBER:

1

VERSION DATE:

12/4/18

STUDY SUMMARY:

Investigational Agent(s) (Drugs or Devices)	Primera TENS/NMES Unit with HAN Waveform by Chattanooga
IND / IDE / HDE #	
Indicate Special Population(s)	 Children  Children who are wards of the state  Adults Unable to Consent  Cognitively Impaired Adults  Neonates of Uncertain Viability  Pregnant Women  Prisoners (or other detained/paroled individuals)  Students/Employees
Sample Size	70
Funding Source	Society of Family Planning Research Fund
Indicate the type of consent to be obtained	 Written  Verbal/Waiver of Documentation of Informed Consent  Waiver of HIPAA Authorization  Waiver/Alteration of Consent Process
Site	 Lead Site (For A Multiple Site Research Study)  Data Coordinating Center (DCC)
Research Related Radiation Exposure	 Yes  No
DSMB / DMC / IDMC	 Yes  No

STU#:

OBJECTIVES:

- Primary Outcome: Self-reported pain on 100mm VAS immediately following dilator placement
- Secondary Outcomes:
 - Self-reported pain at dilator exchange (if applicable)
 - Amount of time (in minutes) spent in clinic following dilator insertion
 - Self-reported highest level of pain between dilator placement and D&E
 - Number and type of adjunctive pain medications used
 - Patient acceptability

The hypothesis is that use of TENS will decrease pain by 20mm on VAS during initial dilator placement prior to dilation and evacuation, improving patient's overall pain management

BACKGROUND:

Dilation and Evacuation is the most common method of second trimester abortion. Studies have shown that adequate cervical preparation is necessary for the procedure to be performed safely and reduce the risk of complications. However, in the majority of cases the placement of these dilators is done with minimal pain management options. Previous research has shown that paracervical block reduces pain with laminaria insertion, (Soon et al., 2017) however despite this, the placement of dilators continues to be, for many, the most painful part of the dilation and evacuation procedure. Several studies have been performed comparing cervical dilation techniques and rated dilator placement pain as moderate to severe (Mercier & Liberty, 2014). Pain following insertion in the hours leading up to the dilation and evacuation has been rated as less severe, but persistent.

Transcutaneous electrical nerve stimulation (TENS) has been used in pain relief since 1965, when Melzack and Walls proposed using electrical stimulation as analgesia based on the gate control theory of pain relief (Johnson, Paley, Howe, & Sluka, 2015; Vance, Dailey, Rakel, & Sluka, 2014). TENS units are small, inexpensive, portable, battery-powered devices which deliver mild, alternating electrical currents via electrodes positioned on the skin near the anticipated dermatomal distribution of pain. The parameters of pulse frequency and pulse intensity are adjustable and linked to TENS efficacy (Vance et al., 2014). They overall have a favorable safety profile. Contraindications include electronic implants, such as cardiac pacemakers and implantable cardioverter defibrillators ("ELECTROPHYSICAL AGENTS - Contraindications And Precautions: An Evidence-Based Approach To Clinical Decision Making In Physical Therapy," 2010).

Two main theories have been proposed regarding how TENS provides analgesia. According to the "gate control" theory, neuromodulation may activate large myelinated afferent nerve fibers in the dorsal horn to inhibit transmission in primary afferent nociceptive fibers. The inhibitory input from the large myelinated afferent fibers is thought to be able to "close the gate" to prevent transmission of pain sensation. (Johnson et al., 2015). The endorphin-mediated theory of pain relief states that a stimulus outside the central nervous system can raise the level of endogenous endorphins and therefore provide analgesia. (Vance et al., 2014)

Despite usage of a paracervical block for pain control, patients still experience significant pain during dilator placement. If TENS provided pain relief for patients undergoing dilator placement prior to dilation and evacuation, this could provide an inexpensive, non-pharmacologic method of pain control that could be widely utilized.

STU#:

STUDY ENDPOINTS:

The study is a single-blinded randomized controlled trial to evaluate pain control using TENS during osmotic dilator placement prior to dilation and evacuation. The intervention group will use an active TENS unit and the control group will use a sham device. The primary objective is self-reported pain on 100mm VAS immediately following dilator placement. The secondary outcomes include self-reported pain at dilator exchange, self-reported highest level of pain between dilator insertion and dilation and evacuation, number and type of adjunctive pain medications used, and patient satisfaction with device. 70 patients will be included in a one to one allotment. The participants will have interaction with the study at two time points. The first is at the time of dilator placement and the second is at the time of dilation and evacuation the following day. No other interactions or long term follow up is needed.

STUDY INTERVENTION(S) / INVESTIGATIONAL AGENT(S):

The device being used in this study is the Primera TENS/NMES Unit with HAN Waveform by Chattanooga. Chattanooga is a manufacturer of rehabilitation equipment for treating musculoskeletal, neurological and soft tissue disorders. It is a division of DJO Global. This device has been approved for pain control management and this is not a novel use for the device.

TENS units are small, inexpensive, portable, battery-powered devices which deliver mild, alternating electrical currents via electrodes positioned on the skin near the anticipated dermatomal distribution of pain.

The TENS units and electrodes will be kept in a locked cabinet in the Family Planning office on the [name], which is the location of the research study and where the primary outcome will be measured.

PROCEDURES INVOLVED:

[figure not shown]
The proposed study is a single-blinded randomized controlled trial studying use of TENS for pain control during initial dilator insertion prior to dilation and evacuation. The participants will be randomized in a 1:1 randomization scheme using opaque, sequentially numbered envelopes following consent. The experimental group will have an active TENS unit – Chattanooga Primera – and the control group will have a sham TENS unit. The sham TENS will be the same unit without the true TENS electrical connections. The true TENS unit consists of the active unit and electrode pads connected to the unit via direct wires. The sham group will be given the active unit and have electrode pads placed but without wire connections. These participants will be told the device is a wireless device. They will also be told they may or may not feel sensation from the TENS. This will allow the device to be powered on and run in the same manner as the active group, but will not allow for electrical transmission between the unit and electrodes.

Based on power calculations, 56 participants are needed to detect a 20mm difference in VAS score with a standard deviation of 30mm. This is based on both minimum clinically significant difference in pain scores as well as previous studies regarding pain during dilator insertion. We will attempt to recruit 70 patients to account for possible TENS unit misuse or study dropout.

Eligible patients will be 18 years of age or older and between 14 weeks and 23 weeks 6 days gestation who meet inclusion/exclusion criteria as listed below. Two electrodes will be placed in

STU#:

the suprapubic area in the bilateral lower quadrants (as shown in the figure at right). The program that will be used is a high frequency (80Hz) program that runs for an hour in duration. It will be initiated 5 minutes prior to speculum placement. Participants will be instructed to increase the amplitude of the current as needed to provide analgesia but avoiding discomfort from the TENS stimulation. All participants will receive a paracervical block of 20mL 1% lidocaine with sodium bicarbonate followed by rigid dilation and dilator placement per standard cervical preparation protocol. Participants will complete 100mm VAS immediately following dilator placement. VAS is a 100mm line on sheet of paper with 0 being no pain and 100mm being worst pain of their life. The number of dilators, type of dilators, and use of adjunctive mifepristone/misoprostol will be according to providers' clinical judgement. Dilator placement will be performed by either Family Planning Fellow, PGY-3 OB/GYN resident, or Nurse Practitioner. All participants will receive prescriptions for twenty tablets of ibuprofen (600mg) and twelve tablets of hydrocodone/acetaminophen 5/325, which is the standard post-dilator insertion pain protocol for this clinic site. Participants will be allowed to leave prior to the end of the initial one-hour program. They will be sent home with instructions of how to run the TENS unit as needed for pain control.

Following the initial hour of use patients can re-activate the TENS unit as often as desired, using the same program. Participants will be given a log to record when TENS unit was used and whether additional pain medications were taken (attached). They will return their completed log and bring pill bottles on the day of surgery to confirm medications used.

Of note, in our practice a second set of cervical dilators is often placed 6 hours after first set in patients over 20 weeks gestation. During this placement the first set is removed, further rigid dilation is performed, and new dilators are placed per standard cervical preparation protocol. Pain score on 100mm VAS will be recorded following this dilator placement as well as a secondary outcome. Participants will run the TENS unit in the same manner as the initial dilator placement for dilator exchange.

On the day of surgery participants will record their highest interval pain score on 100mm VAS. They will also be asked their satisfaction with the TENS device. The TENS unit will be returned on the day of surgery.

The investigative procedures in this study are as follows:

- 100mm VAS immediately following dilator placement
- 100mm VAS immediately following dilator exchange (if applicable)
- 100mm VAS in the preoperative area rating highest pain level in the interval between dilator placement and surgery
- Log detailing when pain was felt in pre-operative interval period, TENS use or nonuse, and use or nonuse of adjunctive pain medication
- 5 Point Likert Scale determining patient satisfaction with TENS (attached)
- Demographic information sheet (attached)

VAS scoring and Log details will be completed on paper. Likert scale and demographics will be collected on tablets.

There are no plans for long-term follow up.

STU#:

DATA AND SPECIMEN BANKING

No data or specimens will be banked for future use.

SHARING RESULTS WITH PARTICIPANTS

Study results will be shared with the participants upon request. This request can be made at any point within the study time period.

Study results will be disseminated within the medical community via scientific publication in a peer-reviewed journal once study completion, data analysis, and manuscript approval has been achieved.

STUDY TIMELINES

The study will begin in March 2019 with participant recruitment. It is anticipated, based on a typical clinic volume of 400 patients requiring osmotic dilator placement prior to dilation and evacuation, that recruitment will take 12 months. Primary data analyses will then take place over the next two months, with plan to complete analyses by May 2019. Manuscript preparation, submission, and approval/publication will then occur.

An individual's participation in the study will be for no longer than 48 hours, which is the maximum amount of time between dilator placement and dilation and evacuation procedure. No further follow up will be required by the patient.

INCLUSION AND EXCLUSION CRITERIA

Inclusion Criteria:

1. Women \geq 18 years of age
2. Gestational age between 14 weeks and 23 weeks 6 days
3. Willing and able to sign an informed consent in English
4. No contraindications to TENS

Exclusion criteria

1. Incarceration
2. Preterm Premature Rupture of Membranes or evidence of intra-amniotic infection
3. Presence of implanted cardiac device
4. Lack of sensation to touch on area of electrode placement
5. Prior TENS use
6. Opioid dependence

All patients between 14 weeks and 23 weeks 6 days gestation who schedule an appointment for a Dilation and Evacuation procedure with Northwestern Family Planning will be reviewed for study eligibility by the study team. All patients will be asked by clinical staff when scheduling an appointment if they have an implanted cardiac device or have used a TENS unit in the past. If eligibility criteria are met, then the patient will be approached regarding this study during the initial consultation appointment following description of dilator insertion procedure.

VULNERABLE POPULATIONS

The population being studied is pregnant women who have previously decided to have a termination of pregnancy or have an intrauterine fetal demise. They will confirm their decision for termination and consent to the termination procedure prior to being approached for study participation and subsequent TENS unit placement. TENS units have previously been studied

STU#:

during labor without adverse effects on the fetus. Therefore, the only potential risk would be patient discomfort from the TENS or allergic reaction to the electrode pads. These risks are rare and short-lived. Any fetal risk that has not previously been identified would be insignificant, as termination of pregnancy will occur 24-36 hours later.

PARTICIPANT POPULATION(S)

Accrual Number:	Category/Group: (Adults/Children Special/Vulnerable Populations)	Consented: Maximum Number to be Consented or Reviewed/Collected/Screened	Enrolled: Number to Complete the Study or Needed to Address the Research Question
Local	Pregnant Women	70	70
Study-wide			
Total:		70	70

RECRUITMENT METHODS

Study participants will be recruited at the Family Planning Clinic at Northwestern Memorial Hospital in Chicago, IL. This study will be registered with ClinicalTrials.gov per protocol. Participation will be completely voluntary. The Family Planning Clinic population is highly variable and includes patients with both Medicaid and private insurance. It includes patients referred from the greater Chicagoland area as well as from nearby states with more prohibitive abortion legislation. This clinic performs about 400 dilation and evacuation procedures requiring dilator placement per year.

Patients will be approached for informed consent by a study team member following determination of eligibility at the initial clinic termination consultation appointment at the Northwestern University Family Planning Clinic. No outsourced advertising for the study will be done.

COMPENSATION FOR PARTICIPATION IN RESEARCH ACTIVITIES

No compensation will be provided for the patients to participate in this study

WITHDRAWAL OF PARTICIPANTS

Participants may choose to discontinue participation at any time.

A participant would be discontinued from this study if they opted to discontinue the TENS unit prematurely during initial dilator placement or if an unexpected allergy to the electrode pads was noted during initial placement. Participants would be excluded from secondary analyses if they did not complete their pain log or agree to report pain/satisfaction with TENS on day of surgery, but would still be included in the primary analyses.

RISKS TO PARTICIPANTS

STU#:

Minimal risk to participants is anticipated with this study protocol.

The physical risk of this study is that the TENS may create a mildly uncomfortable sensation across the lower abdomen. The study participant will be instructed to increase the intensity of the TENS to provide analgesia without excessive discomfort from the unit, however, some discomfort may be felt for a short period of time as the participant is increasing and decreasing the intensity of the TENS. This discomfort is reversible, however, by decreasing the intensity or discontinuing use of the device. The participant may also have a contact allergic reaction to the electrode pads. This contact allergy is short lived and is easily treated with topical corticosteroids.

POTENTIAL BENEFITS TO PARTICIPANTS

If, as we anticipate, use of TENS improves pain control during dilator insertion, this would provide an inexpensive, non-pharmacologic method of analgesia with few contraindications. This could improve the patient experience during a necessary but extremely uncomfortable part of the abortion process.

DATA MANAGEMENT AND CONFIDENTIALITY

Data will be managed using REDCap. All data will either be entered directly into REDCap (with data collected on tablet) or will be entered manually by the primary investigator or research assistant. The paper forms and iPads will be stored in a locked cabinet in a locked office only accessible to the primary investigator and research assistant. All paper forms will be shredded in HIPAA bins following data entry.

Study participants will be compared on baseline characteristics using appropriate statistical methods depending on normal distribution (student t-test or chi-squared test) or non-normal distribution. Primary and secondary outcomes will be measured using appropriate statistical analyses for continuous or categorical data. A two-tailed p value of less than or equal to 0.05 will be considered statistically significant.

The number of subjects needed to show a 20mm reduction on VAS with a standard deviation of 30mm is 56, or 28 per arm. To account for subject discontinuation we will attempt to recruit 70 participants.

According to previous studies the minimum clinically significant difference in VAS is 15mm, however, this is within the standard deviation of typical VAS scores of pain during laminaria insertion and could confound study results. Soon et al previously used a 25mm reduction on VAS to calculate power in a previous study examining pain control during dilator insertion using paracervical block. We have chosen to use a 20mm reduction on VAS as this difference has shown significant in previous pain management research studies and we believe this to be a difference that will alter clinician practice patterns.

PROVISIONS TO MONITOR THE DATA TO ENSURE THE SAFETY OF PARTICIPANTS

This study does not involve more than minimal risk to the participants

PROVISIONS TO PROTECT THE PRIVACY INTERESTS OF PARTICIPANTS

On the day of their pre-operative abortion consultation appointment, a study team member will approach eligible patients regarding study enrollment. The questions they are asked regarding

STU#:

personal health information and demographics are questions that would be asked regardless of study participation.

The participants will enter their demographic information directly onto the iPad themselves or can have the research team enter it for them. They will be assured that their information will be protected as personal health information. Once enrolled, all participants will be given a study identification number. No PHI will be used to identify the participants moving forward within the study period.

COMPENSATION FOR RESEARCH-RELATED INJURY

N/A

ECONOMIC BURDEN TO PARTICIPANTS

No undue economic burden is anticipated for participants. Participants are not responsible for any costs for this research. Insurance will be billed for dilation and evacuation procedure per standard clinical practice.

CONSENT PROCESS

The consent process will take place in a private exam room following the abortion consultation prior to dilator placement. No waiting period will take place between informing the participant of the study and obtaining informed consent. The participant can discontinue involvement in the study at any time by notifying the study team. The individuals listed in the application will be directly responsible for the consent process. The minimum anticipated amount of time devoted to the consent process is 20-30 minutes. Participants will receive the same pain medication regimen whether they consent to the study and are in the control or study cohort or if they decline study participation. Eligible patients will be asked throughout the consent process if they understand the study and if they have any questions. They will also be asked to repeat in their own words what the study entails following the description of the study and consent discussion. Written consent will then be obtained.

WAIVER OR ALTERATION OF CONSENT PROCESS (consent will not be obtained, required information will not be disclosed, or the research involves deception)

N/A

PROTECTED HEALTH INFORMATION (PHI AND HIPAA)

This research will use some medical record information (see attached demographics form). This information will be de-identified and attributed to a study ID number after consent is obtained. Patients will sign a HIPAA Authorization form at the time of consent.

NON-ENGLISH SPEAKING PARTICIPANTS

N/A

QUALIFICATIONS TO CONDUCT RESEARCH AND RESOURCES AVAILABLE

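### Participant blinding is at high risk and is never tested, and the wireless statement made to sham participants conflicts with the N/A in the consent-alteration section

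*Combined protocol and SAP*

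**What the plan says.** Study Endpoints describes the design: "The study is a single-blinded randomized controlled trial to evaluate pain control using TENS". It does not say who is blinded; the use of a sham implies the participant. The same section sets the endpoint: "The primary objective is self-reported pain on 100mm VAS immediately following dilator placement".

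Procedures Involved describes the two kits. Active: "The true TENS unit consists of the active unit and electrode pads connected to the unit via direct wires". Sham: "The sham group will be given the active unit and have electrode pads placed but without wire connections". It adds "These participants will be told the device is a wireless device", and then "They will also be told they may or may not feel sensation from the TENS". The sham unit powers on and runs, but no current reaches the pads.

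The program starts five minutes before speculum placement, and the instruction on intensity is "Participants will be instructed to increase the amplitude of the current as needed to provide analgesia", short of discomfort. The participant marks the VAS immediately after dilator placement, takes the unit home and may re-run it.

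The list of investigative procedures at the end of Procedures Involved contains VAS scores, a log, a satisfaction scale and a demographics sheet. It has no question about perceived assignment.

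The Waiver or Alteration of Consent Process section, whose heading covers cases where "required information will not be disclosed, or the research involves deception", is answered N/A. In the Study Summary the matching consent box is unticked; only written consent is ticked.

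**The concern.** Active TENS is normally felt, and the participant is told to raise it until it helps. A sham participant given the same instruction raises a dial and feels nothing, with pads visibly attached to nothing. That amounts to a self-test of allocation in the minutes before the primary score is recorded.

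Because the endpoint is a self-rating of pain, any difference in expectation between arms goes straight into the estimated treatment effect, most plausibly in favour of TENS. Three of the five secondary outcomes listed under Objectives (pain at exchange, worst interval pain, acceptability) are exposed in the same way. With no blinding check, the trial would have no data with which to answer this criticism of a positive result.

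Separately, telling a participant that a disconnected unit is wireless is untrue. A protocol that scripts this and also records that deception does not apply contradicts itself, whether or not the masking works.

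**Working it through.** **1. The arms side by side, as written**

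| Feature | Active | Sham | Source |
|---|---|---|---|
| Unit | powered, running | powered, running | Procedures Involved |
| Leads | wired to pads | no wires | Procedures Involved |
| Current at pads | yes | none | Procedures Involved |
| Told the unit is wireless | not stated | yes | Procedures Involved |
| Told sensation may be absent | not stated | yes | Procedures Involved |
| Adjusts own amplitude | yes | yes | Procedures Involved |
| Prior TENS experience | excluded | excluded | Inclusion and Exclusion Criteria |

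The sentence on sensation takes its subject from the preceding sentence about the sham group. Nothing says that the active arm hears it, and nothing says that it does not. Risks to Participants expects that some discomfort may be felt while intensity is being adjusted, so the protocol itself assumes that active current is perceptible.

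**2. The plan's own figure.** Data Management and Confidentiality gives 28 per arm (56 in total) for a 20 mm difference, SD 30 mm, with a two-tailed 0.05 test; power is not stated. By n per arm = 2(z_α + z_β)²·SD²/δ², where 30²/20² = 2.25:
- two-sided 0.05, assumed 80% power: 2(1.960 + 0.842)² × 2.25 = 35.3, so 36 per arm (72), not 56;
- one-sided 0.05, 80% power: 2(1.645 + 0.842)² × 2.25 = 27.8, so 28 per arm;
- two-sided 0.05, 70% power: 2(1.960 + 0.524)² × 2.25 = 27.8, so 28 per arm.

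The recruitment target follows from a 20% loss: 56/0.8 = 70. The sample-size mismatch is a separate matter. The blinding point does not depend on it and uses only the SD and the two possible arm sizes, 28 and 35.

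**3. Illustration of the stake.** Assume no true effect, and that imperfect blinding shifts reported pain by b mm in favour of active. The b values are assumptions, because the documents give none. For a two-sample t-test, the noncentrality is b/(SD·√(2/n)):
- n = 28: standard error 30 × √(2/28) = 8.02 mm, 54 df;
- n = 35: standard error 30 × √(2/35) = 7.17 mm, 68 df.

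| Assumed shift b | Share of 20 mm target | P(p≤0.05), 28 per arm | P(p≤0.05), 35 per arm |
|---|---|---|---|
| 0 mm | 0% | 5.0% | 5.0% |
| 5 mm | 25% | 9.4% | 10.6% |
| 10 mm | 50% | 23.2% | 28.0% |
| 15 mm | 75% | 45.1% | 54.1% |

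The 28-per-arm column matches the plan's evaluable number; the 35-per-arm column assumes no losses. A larger trial makes a fixed bias more likely to reach significance.

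**4. The consent entry.** Procedures Involved scripts a statement that is false for a unit with no connection to its pads. The section whose heading names deception says N/A, the Study Summary box is unticked, and no debrief is described in the protocol text. These entries cannot all stand.

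**The case against.** The strongest reply is that the sham may work. Women with prior TENS use are excluded and are asked about it at scheduling, so participants have no reference for what the device should look or feel like. Nothing in the protocol lets a participant see the other arm's kit. Someone handed a running unit, told it is wireless and told that she may feel nothing, need not conclude that it is inactive. Allocation is by opaque, sequentially numbered envelopes after consent, and all participants get the same paracervical block and analgesic prescriptions. All of this stands. It is why the point is one of high risk and not of demonstrated failure.

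A reader might go further and infer that the kit and script reveal allocation, so that the blinding claim is not credible. The documents do not support that. The wires alone need not unblind a TENS-naive participant. The consent form is not in the review copy, and the Consent Process section mentions only control and study cohorts, so what participants learn about a sham cannot be checked.

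A reader might also infer that a provider who can see the wiring contradicts the design. It does not: single-blinding is compatible with an unblinded provider, and the participant marks the VAS herself. The gap is that no one's blinding status is defined.

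Nor are nearly all secondary outcomes subjective. Clinic time is not a pain rating, and medication use is confirmed against pill bottles.

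What the reply does not meet is the amplitude instruction. Inexperience does not stop a participant noticing that nothing changes as she turns the unit up, and no data would show whether masking held.

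**Conclusion.** The concern holds in this form: participant blinding is at high risk and untested, and expectation bias, if present, would probably favour TENS on the primary endpoint. Existing safeguards reduce the risk without removing it. The size of any bias is unknown. The 9–23% (28 per arm) and 11–28% (35 per arm) false-positive figures are conditional on an assumed 5 to 10 mm shift, no true effect and SD 30 mm. They show sensitivity and are not estimates. They also do not mean that a positive result could never be told apart from unblinding.

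Whether the two arms hear different scripts about sensation needs clarification; the text allows, but does not prove, a difference. The conflict between the wireless statement and the N/A entry is certain on the page and must be corrected regardless of how the blinding question is settled.

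**What to change.** 1. **Leads.** Use identical-looking wired lead sets in both arms, with the sham set open-circuit, so that units power on and look the same. The wireless statement can then be deleted.
2. **Script and definition.** Give both arms the same wording, including that sensation may or may not be felt, and state in Study Endpoints and Procedures Involved who is blinded.
3. **Blinding check.** Ask each participant which device she thinks she had, and why, right after the primary VAS is marked, and report the answers by arm. A guess collected only on the day of surgery follows home use and would not describe blinding when the primary score was given. Acknowledge as a limitation that felt stimulation may still unblind some active participants.
4. **Consent entry.** Reconcile Procedures Involved with the Waiver or Alteration of Consent Process section and the Study Summary box. Either remove the wireless statement, or complete that section, tick the box and add a debrief.

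The cost is a set of modified leads, edits to the script and one extra question, with no added visits or staff. Matched leads address only the visible difference, so masking will remain imperfect. These changes need to be in place before enrolment, because masking cannot be restored or measured afterwards.

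### Participants who stop TENS during initial placement appear to be left out of the primary analysis, which opens the randomised comparison to selection bias, plausibly but not certainly towards TENS

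*Combined protocol and SAP*

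**What the plan says.** All references are to the combined protocol and SAP.

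- **Randomisation.** Procedures Involved: "The participants will be randomized in a 1:1 randomization scheme using opaque, sequentially numbered envelopes following consent". The Consent Process section puts consent before dilator placement, so anything that happens during placement is post-randomisation.
- **Discontinuation.** Withdrawal of Participants: "A participant would be discontinued from this study if they opted to discontinue the TENS unit prematurely during initial dilator placement". The same sentence gives a second trigger, a reaction to the pads at that stage. The rule names no arm.
- **Who is kept.** The next sentence there takes participants with an incomplete log or no day-of-surgery report out of the secondary analyses, "but would still be included in the primary analyses". Nothing equivalent is said about those who stop the device.
- **Sample size margin.** Procedures Involved: "We will attempt to recruit 70 patients to account for possible TENS unit misuse or study dropout". Data Management and Confidentiality: "To account for subject discontinuation we will attempt to recruit 70 participants".
- **Difference between arms.** The sham unit is switched on "but will not allow for electrical transmission between the unit and electrodes". Under Risks to Participants: "The physical risk of this study is that the TENS may create a mildly uncomfortable sensation across the lower abdomen". That section names stopping the device as one remedy and lowering the intensity as another.
- **Analysis.** Data Management and Confidentiality promises appropriate methods for continuous or categorical data and a two-tailed 0.05 level. It defines no analysis set and gives no rule for a missing VAS.

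**The concern.** Randomisation protects the comparison only if the people analysed are those who were randomised, or if losses are unrelated to arm and outcome. Here the trigger for loss can depend on both. Stimulation discomfort exists in one arm only, and a participant in severe pain may be more inclined to have the device removed. If such people leave the active arm in greater numbers, the trial compares those who tolerated TENS with a less selected sham group. The estimated benefit is then too large and the false-positive rate exceeds 5%.

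The loss is avoidable. The primary VAS is marked immediately after placement, at the same visit, so stopping the device does not prevent its collection. If it is not collected, no later analysis can recover it.

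**Working it through.** **1. Does discontinuation mean exclusion from the primary analysis?** Three places point that way. The Withdrawal section expressly keeps another group in the primary analysis, a contrast that has little purpose if discontinued participants are kept too. Procedures Involved counts device misuse as a reason for extra recruitment, and misuse costs sample size only if misusers are not analysed. Data Management gives discontinuation as the reason for the same margin. This is inference, but nothing in the text contradicts it.

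**2. The plan's own figures.** Inputs: difference 20 mm, SD 30 mm, 56 needed, 70 recruited. Power is not stated; 80% is assumed.

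- n per arm = 2 × (z_alpha + z_power)² × (30/20)².
- One-sided 0.05: 2 × (1.645 + 0.842)² × 2.25 = 27.8, so 28 per arm and 56 in total. This matches the plan.
- Two-sided 0.05, the level the plan states: 2 × (1.960 + 0.842)² × 2.25 = 35.3, so 36 per arm and 72 in total. This is a separate matter, but it means that 70 leaves no real room for exclusions.
- Margin: 70 − 56 = 14, and 14/70 = 20%.

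**3. Size of the shift, in general.** If k of 35 active participants are removed and their mean VAS exceeds that of the retained by D, the active mean falls by (k/35) × D. The documents give neither k nor D. For D from 10 to 40 mm:

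- k = 3: 0.9 to 3.4 mm
- k = 5: 1.4 to 5.7 mm
- k = 7: 2.0 to 8.0 mm

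**4. Size under a stopping model.** Assumptions: no true effect, 35 per arm, normal VAS with SD 30, and a latent tendency to stop that correlates rho with VAS. The k participants with the highest tendency are removed. The expected shift in an arm is rho × 30 × S_k/(35 − k), where S_k is the expected sum of the k largest of 35 standard normal values: S_1 = 2.11, S_2 = 3.80, S_3 = 5.24, S_5 = 7.64, S_7 = 9.52. For example, k = 5 and rho = 0.5 gives 0.5 × 30 × 7.64/30 = 3.8 mm. Type I error comes from simulated two-sided t-tests.

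| Removed, active/sham | rho | Spurious difference | Type I error |
|---|---|---|---|
| 3/0 | 0 | about 0 | about 5% |
| 3/0 | 0.5 | 2.4–2.5 mm towards TENS | about 6.7% |
| 5/0 | 0.5 | 3.8 mm towards TENS | about 8.5% |
| 7/0 | 0.5 | 5.1 mm towards TENS | about 10.6% |
| 5/3 | 0.5 | 3.82 − 2.46 = about 1.4 mm towards TENS | about 6.4% |
| 5/5 | 0.5 | about 0 | 5–6% |
| 2/5 | 0.5 | 3.82 − 1.73 = about 2.1 mm against TENS | about 6.7% |

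With only one or two active stops and none in sham, the shift runs from 0.3 × 30 × 2.11/34 = 0.6 mm to 0.7 × 30 × 3.80/33 = 2.4 mm, with type I error about 5–7%. At the far end, 7/0 with rho 0.7 gives 0.7 × 30 × 9.52/28 = 7.1 mm and about 17%.

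**5. Power for 20 mm (two-sided t-test).** With 35 against 35 it is 78.5%. With 28 against 35 (7 active participants lost) it is 73.5%.

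**The case against.** The strongest reply is that the plan never says these data are dropped. Being discontinued from a study need not mean that a VAS is refused or ignored. That is correct, and exclusion should be described as implied. The reply does not remove the problem. With no analysis set defined, the choice would be made later, in a trial described only as single-blinded.

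A second reply is that the rule is even-handed. Sham participants also wear pads and may react to them, and they may stop because of pain or lack of relief. If TENS works, pain-driven stopping could be commoner in sham. Active participants can lower the intensity instead of stopping, and the Vulnerable Populations section describes the risks as rare and brief. This stands, and it limits the point. A reader might infer that the rule removes only active-arm failures and so must favour TENS. The documents do not support that: the rule names no arm, no stopping rates are given, and the 2/5 case reverses the sign.

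A reader might also infer that the rule cuts power to 69%. That figure needs 28 per arm, meaning loss of all 14 in the margin. The margin covers ordinary dropout as well as misuse, and no analysis rule recovers true dropouts.

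**Conclusion.** The concern holds in a limited form. The plan sets a post-randomisation, tolerance-related discontinuation rule just before the primary endpoint, implies that those affected are not analysed, and has no intention-to-treat set or missing-data rule to offset it. The primary comparison is therefore open to selection bias. Bias towards TENS is the more plausible direction, because the documents identify one reason for stopping that exists only in the active arm, but it is not certain.

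The size rests wholly on assumed stopping counts and an assumed link with pain. At a correlation of 0.5, it runs from about 3.8 mm of false benefit (5/0) through nothing (5/5) to about 2.1 mm against TENS (2/5). One or two active-only stops would matter little. The point should still be settled before data collection, because a VAS that was not collected cannot be recovered.

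**What to change.** Limit the change to data collection and analysis. Whether the device continues to be used after a problem remains a clinical decision, and the right to withdraw is unchanged.

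1. Replace the discontinuation sentence with: *Stopping the device early, using it incorrectly or having a pad reaction does not end data collection. Unless they withdraw consent, these participants are asked to complete the VAS after dilator placement and are analysed in the arm to which they were randomised.*
2. Define the primary analysis set as all randomised participants with dilators placed, by assigned arm. Report by arm how many did not reach placement.
3. State how a missing primary VAS is handled, including a sensitivity analysis in which the assumed missing values differ between arms.
4. Report early stops and their reasons by arm, as a tolerability result.
5. Keep any per-protocol analysis as supportive.

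The cost is a few protocol sentences and one mark on paper at a visit already taking place. The estimated effect may be somewhat smaller, because it will include people who did not tolerate or use the device as intended.
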